## **Data Analyses and Interpretation**

General Statistical Approaches. Data will be analyzed descriptively and analytically. Descriptive statistics (means and standard deviations for continuous and proportions/counts for categorical outcomes) will be used to describe outcomes at baseline. Weighted generalized estimating equations (WGEE) will be employed, with appropriate link functions depending on the type of the response (e.g., identity for continuous and logit for binary outcome), to examine longitudinal changes in an outcome and longitudinal association between outcomes in regression analysis, controlling for covariates for Aims 1-2. Unlike parametric models such as generalized linear mixed-effects models (GLMM), the semi-parametric WGEE requires no distribution assumption and yields valid inference for a broader class of data distribution under the missing at random mechanism^123. WGEE provides valid inferences under the missing at random (MAR) mechanism^124. We will use WGEE to test the missing completely at random (MCAR) assumption and will use the generalized estimating equations (GEE), if the MCAR is not rejected. GEE involves fewer parameters and provides more efficient inference than WGEE. Given the small sample size for Aims 1-2, we will complement the usual asymptotic inference with clustered bootstrap to improve inference validity and report the bootstrap inference if it differs from its asymptotic counterpart. We set  $\alpha$ =0.05 for all analyses and use Holm-Bonferroni adjustments for <= 5 tests and False Discovery Rate (FDR) for > 5 tests. When correlated outcomes are analyzed (e.g., outcomes in related domains), corrections will be calculated based on the effective number of independent tests that account for correlations between the outcomes. Whenever possible, effect size will be reported in addition to point and interval estimates. All analyses will be performed using the latest versions of R^129 and SAS. Hypothesis Testing. For Aim 1, separately for OT and saline placebo sessions, we will compare changes in ratings of pain over time between the OT and control arm using WGEE, where time (one binary indicator) will be the predictor, controlling for covariates. A significant time effect, tested using appropriate linear contrasts, will support the hypothesis that the OT injection has effects on the outcome. We will follow with *post hoc* analyses to estimate the effect size of the OT injection. For Aim 2, we will apply the same approach in Aim 1 to pleasant touch outcome. Age and race/ethnicity will be included as potential covariates in all analyses.

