# Sessions 1 (after baseline) and 2 will occur at the ACTRI and will take approximately 1 hour each to complete.

## Participant Randomization:

The schedule of randomization will be created and accessed by an ACTRI pharmacist only. Males and females will be randomized without replacement across a block of 20 codes (assuming 20% attrition) using an Excel-based random number generator. All subjects will receive OT in one session and saline placebo in the other in this within-subject cross-over study. Subjects will be randomized to one of two session orders (Session 1 OT and Session 2 saline; Session 1 saline and Session 2 OT). Randomization will be stratified so that each sex will have their respective list of randomization codes. Session order (blinded code) will be tracked in the Screening/Enrollment Log maintained by the study coordinator(s) and identity of the orders will be revealed by the pharmacy at the conclusion of the study.

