## Timeline

To ensure drug clearance, Sessions 1 and 2 (OT; saline placebo or saline placebo; OT) will be separated by more than two days according to the participant and experimenters' availability. After providing written consent (active enrollment), subjects will have 4 months to complete Sessions 1-2. Sessions will be offered to healthy volunteers until our sample size of 20 healthy volunteers has been reached. These sessions will be filled on a first-come-first-served basis.

1-2 years will be required for recruitment, data collection, and analysis.

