# Sample Size Determination & Power

We expect that pleasantness ratings of C-LTMR-optimal touch will be significantly increased after local OT injection and that pain perception will be reduced. In published studies, differences in postsurgical pain after local infiltration with OT versus control resulted in very large mean differences in VAS pain ratings of Cohen's d = 3 to 4.5. In spinal nerve ligation (SNL) model rats, interplantar injection of OT versus control resulted in mean differences in paw withdrawal threshold of Cohen's  $d = 13.8^{19}$ . In addition, intranasal oxytocin (24IU) increases pleasantness of touch stimuli (especially driven by negative stimuli), with an estimated Cohen's d of  $\sim 3^{23}$ . Although these are very large effect sizes, accounting for sampling variability and differences in proposed study design (acute pain; healthy adults; subcutaneous OT administration), we powered the study to detect a large effect size of d = 0.8. Assuming a within-subject correlation of 0.5 and an attrition rate of 25%,

the proposed sample size of N = 20 will provide 0.8 power to detect an effect size as small as d = 0.8 based on a two-sided  $\alpha = 0.05$ .

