
## **10. HUMAN SUBJECTS**

## **Subject Population**

A total of 20 healthy adults, ages 18-65, will complete two separate test sessions in a within-subject crossover study. Equal numbers of males and females will be recruited. Data will be analyzed to determine if sex is a significant predictor of study outcomes. We will include all genders, races, and ethnicities.

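### A low-power MCAR test chooses between GEE and WGEE, and session-by-session models leave the other session's data unused; the likely bias is small, but the switch should go

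*Combined protocol and SAP*

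**What the plan says.** Under Data Analyses and Interpretation, the plan adopts weighted GEE and gives the reason: "WGEE provides valid inferences under the missing at random (MAR) mechanism". It then adds a data-driven switch: "We will use WGEE to test the missing completely at random (MCAR) assumption and will use the generalized estimating equations (GEE" when MCAR is not rejected, on the ground that GEE has fewer parameters and is more efficient. The section names no missingness model, no variables for the weights, no test level specific to the switch and no working correlation. It does not say whether the switch runs once or for each outcome. The Aim 1 and Aim 2 models are fitted separately for the oxytocin and the saline session, each with a single pre/post indicator plus covariates. A clustered bootstrap supplements the asymptotic inference because the sample is small.

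The figures for attrition differ between sections. Sample Size Determination & Power has "Assuming a within-subject correlation of 0.5 and an attrition rate of 25" per cent. Participant Randomization has "randomized without replacement across a block of 20 codes (assuming 20% attrition". Subject Population has "A total of 20 healthy adults, ages 18-65, will complete two separate test sessions in a within-subject crossover study". The Timeline has "Sessions will be offered to healthy volunteers until our sample size of 20 healthy volunteers has been reached", without saying whether that means enrolled or completed.

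**The concern.** The switch treats failure to reject MCAR as permission to drop the weights, and the weights are the only part of the plan for which MAR validity is claimed. With a handful of leavers, failure to reject is the expected result whether or not dropout depends on what was seen in Session 1. The test therefore says little, yet it decides the estimator. If it is run outcome by outcome, different endpoints could end up with different estimators.

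A second feature adds to this. Pre-testing, injection and post-testing take place in one visit of about an hour, and the two visits are more than two days apart. Most attrition is therefore likely to be a missed Session 2, although the protocol does not say so. In a model fitted to one session alone, such a person has neither a pre nor a post value, and the Session 1 ratings are not used there. At stake are a clear, fixed primary estimator, some precision, and the basis for the MAR claim.

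**Working it through.** **1. The plan's own figure.** Inputs from Sample Size Determination & Power: d = 0.8, within-subject correlation 0.5, two-sided alpha 0.05, power 0.8, attrition 25%. The standardised paired difference is 0.8 / sqrt(2 × (1 − 0.5)) = 0.80. Paired t-test power (noncentral t) is 0.790 with 14 completers and 0.821 with 15, so 15 are needed. 15 / 0.75 = 20. The plan's N = 20 reproduces.

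**2. Number of leavers.** 20 × 0.25 = 5 (power section); 20 × 0.20 = 4 (randomization section). The binomial 95% range is 2-9 at 25% and 1-8 at 20%. If 20 means completers, about 5 (20 / 0.80 − 20) to 7 (20 / 0.75 − 20 = 6.7) would leave in addition.

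**3. Power to see a Session 1 difference between stayers and leavers.** Two-sample t-test, noncentrality d / sqrt(1/a + 1/b). For 15 v 5 and d = 0.8 this is 0.8 / sqrt(1/15 + 1/5) = 0.8 / 0.516 = 1.55 on 18 df.

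| Stayers v leavers | 0.5 SD | 0.8 SD | 1.0 SD | Difference for 80% power |
|---|---|---|---|---|
| 15 v 5 | 15% | 31% | 45% | 1.53 SD |
| 16 v 4 | 14% | 27% | 40% | 1.66 SD |
| 20 v 7 | 20% | 42% | 59% | 1.29 SD |

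If the test is run within each treatment session, only about 10 people have that session second and 2 or 3 would be missing. Power at 0.8 SD is then 15-18%.

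**4. The switch, by simulation.** Assumptions: N = 20, normal ratings, correlation 0.5 between sessions (borrowed from the power section), Session 2 missing by a logistic model on the standardised Session 1 rating, runs with fewer than two missing excluded, about 3,700-4,000 usable runs per scenario. The odds ratios are assumed; the documents give none.

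| Attrition | Odds ratio per SD | MCAR rejected: Wald | MCAR rejected: likelihood ratio |
|---|---|---|---|
| 25% | 2 | 9% | 27% |
| 25% | 3 | 18% | 49% |
| 25% | 4 | 24% | 63% |
| 20% | 2 | 6% | 25% |
| 20% | 3 | 13% | 46% |

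At 25% attrition the rule picks unweighted GEE in 100 − 27 = 73% to 100 − 9 = 91% of trials at odds ratio 2, and in 51-82% at odds ratio 3. Only with stronger dependence and the likelihood-ratio form does rejection become the more common result.

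**5. Consequence for estimates.** Bias in the Session 2 mean, 25% attrition, odds ratio 1.5 / 2 / 3:
- unweighted GEE: −0.05 / −0.08 / −0.11 SD;
- the switching rule (likelihood-ratio test): −0.03 / −0.045 / −0.05 SD;
- WGEE weighted on the Session 1 rating: −0.005 / −0.006 / −0.014 SD;
- maximum likelihood on both sessions: within 0.005 SD of zero.

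The sampling SD is about 0.26-0.27, so the switching rule's largest bias here is about 0.05 / 0.27 = 0.19 of a standard error. For the oxytocin-saline contrast, unweighted GEE bias is 0.02-0.04 SD, smaller because session order is randomised. For the within-session pre/post change, which the Aim models test, bias is at most about 0.01 SD: whoever is missing loses both values, and selection on level largely cancels in the difference.

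**6. Precision.** For the oxytocin-saline contrast at odds ratio 3, the variance of independence GEE relative to a joint model is 1.11-1.14 at between-session correlation 0.5 and 1.31-1.40 at 0.7. Exchangeable GEE on both sessions gives 0.995 and 1.008, so the loss disappears.

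**The case against.** The strongest reply is that little harm is shown. Bias is small against sampling error, and close to zero for the plan's own pre/post change. No failure of type I error or coverage has been demonstrated, and the dropout strengths are assumed. All of that stands, and it limits the weight of the point. The near-zero bias for change does assume that a person's level is unrelated to later change; otherwise some bias could appear.

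The plan also chose a semi-parametric method deliberately, to avoid distributional assumptions, and added a bootstrap. That is a defensible choice, and requiring a mixed model with particular degrees of freedom would be partly preference.

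Several stronger readings are tempting but unsupported:
- A reader might infer that the plan cannot achieve MAR validity because there is nothing to weight on. Session 1 ratings, questionnaires given before or during Session 1, age and race/ethnicity are all known for someone who misses Session 2, and weight variables need not be in the outcome model. Weights on Session 1 removed nearly all the bias. The gap is that no weight model is stated.
- A reader might infer that five people will miss a whole session. The documents give 20%, 25% and 20 completers in different places, and none defines attrition as a missed session. Section 15 (Heat and sensory stimuli) lets a participant stop pain stimulation and be dismissed, which could leave a pre value without a post value.
- A reader might infer a built-in variance penalty of 11-40%. That figure assumes independence across sessions. It does not arise with exchangeable correlation on joint data, and the plan states no working correlation.

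None of this defends the switch itself. An uninformative test still selects the estimator.

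**Conclusion.** The concern holds in a limited form. At this sample size the MCAR test is too weak to choose an estimator: it rejects in about 9-27% of trials at an odds ratio of 2 per SD and 18-49% at 3 with 25% attrition, and slightly less often with 20%. The plan will usually revert to unweighted GEE, for which it claims no MAR validity. Fitting each session separately leaves the other session's data unused in that model, and the weights are unspecified. The expected bias is about 0.02-0.05 SD for session-level means under the switching rule or for the oxytocin-saline contrast, and near zero for within-session change. The cost in precision cannot be fixed without a stated working correlation. These sizes rest on assumed logistic dropout on the Session 1 rating, normal outcomes and whole-session loss. The change is worth considering because it is cheap and removes an arbitrary step; the results are not shown to be seriously at risk without it.

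**What to change.** Delete the MCAR-test switch; if such a test is reported, make it descriptive only. Prespecify one primary model that uses both sessions of all randomised participants, with terms for treatment and session and with within-person correlation. Any of three forms would serve: a linear mixed model, GEE with exchangeable working correlation, or WGEE with a stated weight model that uses Session 1 data. Apply the same form to every outcome. Keep the clustered bootstrap and add a sensitivity analysis in participants who completed both sessions. In the same edit, reconcile the 20% and 25% attrition figures and say whether 20 counts enrolled participants or completers.

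The cost is a revision of the analysis wording and simpler programming, with no change to data collection; it should be made before unblinding. The downside is a working assumption, normality for the mixed model or the correlation structure for GEE, which the planned bootstrap can check.

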## Pain perception:

*Mechanical pain threshold (MPT):* MPT will be determined using weighted pinprick stimuli exerting forces of 8, 16, 32, 64, 128, 256 and 512 mN. Stimuli will be applied for 2s on and 2s off until the first percept of sharpness (pain) is reported.

*Temporal summation:* Temporal summation will be tested using a standard 256mN pinprick stimulus applied for 10 repetitions of 1s each, over the same 1cm^2 area. The participant will provide pain ratings for a single

pinprick and for the 10 repetitions, using the VAS rating scales described above. This procedure will be repeated 3 times and the mean pain rating used.

*Pressure pain threshold (PPT):* PPT will be tested using a pressure algometer placed over the dorsal forearm muscles (e.g. extensor digitorum), and pressure will be increased until pain is reported.

*Heat pain threshold (HPT)*: HPT will be tested using a high-quality QST thermode. To establish HPT, the thermode will be placed on the arm at a baseline of skin temperature (automatically calibrated by the thermode) and will be increased until the stimulus is reported as painful by the participant. The mean of three trials will be taken as the HPT.

*Heat pain ratings:* Three 10s trials of the individually calibrated pain-70 heat stimulus will be rated using the VAS rating scales for pain intensity and (un)pleasantness described above.

*Injection of Oxytocin or saline control:* Either 4mcg/2ml OT *OR* 2ml isotonic saline (0.9% sodium chloride; placebo control) will be injected into the middle of the dorsal forearm. Sessions will be separated by at least 48 hours to ensure drug clearance. Both participants and experimenters will be fully blinded with respect to OT versus saline placebo session/order. OT and saline will be prepared by the Investigational Drug Service at the ACTRI. OT will be prepared by diluting commercially available synthetic oxytocin (OXYTOCIN- oxytocin injection, solution from Fresenius Kabi USA, LLC or equivalent manufacturer supplied by the ACTRI research pharmacy; see uploaded package insert). The injection will be performed by a licensed healthcare provider. Saline placebo will be drawn from SODIUM CHLORIDE- sodium chloride injection, solution from B. Braun Medical Inc or equivalent manufacturer supplied by IDS pharmacy (see uploaded package insert).

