#### Outcome Measure(s)

#### Primary Outcomes:

- Pleasantness ratings of slow (primary) and fast gentle brushing
- Pain perception assessed in response to noxious pinprick (primary), pressure, and heat stimulation.
- Pain intensity and (un)pleasantness will be assessed with visual analog scales (VAS) as follows: pain intensity [anchors "no pain" (far left) to "most intense pain imaginable" (far right)] and (un)pleasantness ["extremely unpleasant" (far left) to "neutral" (middle) to "extremely pleasant" (far right)]. 100-point VAS scales are common, validated, and reliable measures of pain.

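### The small-sample safeguard for the (W)GEE tests is a cluster bootstrap of unstated type, and with 15–20 participants some common types leave a nominal 5% test at about 7–8%

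*Combined protocol and SAP*

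**What the plan says.** Section 9, Data Analyses and Interpretation, makes WGEE the main analysis, or GEE if missingness completely at random is not rejected. It refers to the small sample for both aims and promises to "complement the usual asymptotic inference with clustered bootstrap to improve inference validity and report the bootstrap inference if it differs from its asymptotic counterpart". It does not state the bootstrap type, the number of resamples or what counts as differing. It mentions no bias-corrected variance and no t reference. A citation (125) is attached, but the supplied bibliography ends at 32, so whether that source settles the type cannot be seen.

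The conclusion rests on significance: "A significant time effect, tested using appropriate linear contrasts, will support the hypothesis that the OT injection has effects on the outcome". The models are fitted "separately for OT and saline placebo sessions, we will compare changes in ratings of pain over time", so the clusters in each model are the participants who contribute to that session.

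Three statements bear on how many that is:
- The sample size section has "Assuming a within-subject correlation of 0.5 and an attrition rate of 25" per cent, which leaves 15 of 20.
- The randomization section has "randomized without replacement across a block of 20 codes (assuming 20% attrition", which leaves 16 of 20.
- The Subject Population section has "A total of 20 healthy adults, ages 18-65, will complete two separate test sessions in a within-subject crossover study", which gives 20.

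The lead outcomes include a continuous rating ("Pleasantness ratings of slow (primary) and fast gentle brushing") and pinprick pain. The pinprick threshold takes only a few values: "MPT will be determined using weighted pinprick stimuli exerting forces of 8, 16, 32, 64, 128, 256 and 512 mN".

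**The concern.** With few clusters, the uncorrected sandwich variance is too small on average, and a normal reference ignores the uncertainty in it. Both make the test reject too often and the interval too narrow.

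A cluster bootstrap is a sensible response, but its forms differ. Percentile and bootstrap-SE intervals are built from the spread of resampled means, which has the same downward bias as the sandwich. They would usually agree with a false-positive large-sample result, so the plan's own check would appear to confirm it. A bootstrap-t form rescales by a standard error in each resample and can correct the problem. At stake are the level of the tests that decide both aims and the width of the reported intervals.

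**Working it through.** **Inputs.** Two-sided α = 0.05, N = 20, d = 0.8, within-subject correlation 0.5 and 25% attrition (Sample Size Determination & Power); 20% attrition (Participant Randomization); 20 completing (Subject Population). Assumption, because the plan does not say: the large-sample test is a robust-variance Wald test against the normal distribution.

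**The plan's own figure.** The SD of the within-person difference is √(2(1 − 0.5)) = 1 in outcome-SD units, so the paired effect is 0.8. Analysable n = 20 × 0.75 = 15. The noncentral t with 14 df and noncentrality 0.8√15 = 3.10 gives power 0.821. The stated 0.8 is reproduced. With 20 completers, power is 0.924.

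**Exact level of the large-sample test.** Take a balanced within-person contrast with normal changes d and complete data. The uncorrected sandwich SE is √Σ(d − d̄)²/n, which is √((n−1)/n) times the usual SE. Hence

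level = P(|t with n−1 df| > 1.96·√((n−1)/n)),

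and the interval width relative to the t interval is 1.96·√((n−1)/n) / t(0.975, n−1).

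| n | cut-off | level, uncorrected sandwich | level, n−1 divisor (cut-off 1.96) | width ratio, uncorrected |
|---|---|---|---|---|
| 15 | 1.893 | 7.9% | 7.0% | 1.893/2.145 = 0.883 |
| 16 | 1.898 | 7.7% | 6.9% | 1.898/2.131 = 0.890 |
| 20 | 1.910 | 7.1% | 6.5% | 1.910/2.093 = 0.913 |

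So the uncorrected interval is 9–12% narrower than the t interval. Equivalently, the t interval is 1/0.913 = 1.10 to 1/0.883 = 1.13 times as wide.

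**Simulated levels when there is no effect, n = 15 / n = 20.** Participants are resampled 999 times. The normal and heavy-tailed rows use 30,000 trials (Monte Carlo SE about 0.15 points). The other rows use 12,000 (about 0.25 points). Heavy tails are differences of two exponentials, steps are changes on a seven-level ladder, and the skewed row (one-sided exponential) is a stress case. A dash means not run.

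| Changes | z, uncorrected | percentile | bootstrap-SE | equal-tailed bootstrap-t | symmetric bootstrap-t | corrected sandwich with t |
|---|---|---|---|---|---|---|
| Normal | 7.8 / 7.0% | 8.1 / 7.2% | 7.9 / 7.0% | 5.1 / 5.1% | 4.5 / 4.6% | 4.9 / 5.0% |
| Symmetric heavy tails | 7.8 / 6.8% | 9.5 / 8.2% | 7.9 / 6.9% | 7.9 / 7.4% | 3.8 / 3.8% | 4.7 / 4.5% |
| Steps | 7.2 / 7.7% | 6.2 / 6.4% | – | – | – | 4.8 / 5.5% |
| Strong one-sided skew | 11.8 / 10.4% | 11.4 / 10.0% | – | 5.7 / 5.4% | 6.6 / 6.3% | 8.8 / 8.4% |

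In the skewed case the equal-tailed entry comes from a separate 12,000-trial run. Other runs put it up to about 6.3%, and one 8,000-trial run gave 5.1% at n = 15.

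Under normal changes, the percentile form confirms about 94% of false-positive z results and the bootstrap-SE form about 97–98%.

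**Closer to the planned model.**
- A fitted GEE at n = 15 with age and race as covariates (2,500 trials, SE about 0.6 points) gave 8.8% for the time effect and 8.7% for arm by time, uncorrected. A bias-corrected variance with t on 14 df gave 5.0% and 5.2%.
- WGEE with estimated weights was run with 20 randomised, 10 per order, and 25% lost between sessions (assumed). The OT session then has about 17.4 contributors, in line with 10 + 10 × 0.75 = 17.5. Over four scenarios of 8,000 trials, z gave 7.7–8.2%, percentile 8.0–8.7% and the corrected sandwich with t 5.2–5.5%. Weights were held fixed in the resampling.

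**The case against.** **The large-sample test does not decide the outcome.** If the bootstrap is reported whenever it differs, and the two lead to the same decision otherwise, the decision is always the bootstrap's. This stands, unless some tolerance is allowed before results count as different. A reader might infer that the trial's tests will run at 7–8%. The documents do not support that, because they fix neither the variance, nor the reference distribution, nor the bootstrap type.

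**The authors saw the problem.** They did. A reader might infer that the plan ignores the small sample, but its text says otherwise. The gap is in specification: a bootstrap-t form would already hold about 5% under normal changes.

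**Pinprick thresholds move in steps.** There the percentile bootstrap gives 6.2–6.4%, so an excess of 2–3 points is not general.

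**No method wins everywhere.** This also stands. Under strong one-sided skew the corrected sandwich with t runs at about 8–9%, worse than equal-tailed (about 5.4–6.3%) or symmetric (6–7%) bootstrap-t. Under symmetric heavy tails the equal-tailed form runs at about 7.4–8% and the corrected sandwich with t at about 4.5–4.8%.

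**The multiplicity adjustment absorbs the excess.** It does not, because Holm and FDR take the p-values as valid. By the formula above, a nominal 1% test (Holm's first step with five tests, normal cut-off 2.576) has level P(|t| > 2.576·√((n−1)/n)), which is 2.6% at n = 15 and 2.1% at n = 20.

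**It is a pilot and the excess is modest.** That limits the severity. It does not remove the case for a change of one or two sentences.

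**Conclusion.** The point holds as a gap in specification with a moderate effect. Under the stated assumption, normal changes and complete data, the default test has level 7.1–7.9% at 15–20 participants, or 6.5–7.0% with an n−1 divisor. Percentile and bootstrap-SE bootstraps do not repair this (about 7–8%), whereas bootstrap-t does (about 4–5%). Where the bootstrap and the large-sample result agree, the interval shown may be 9–12% narrower than the t interval.

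It might be inferred that the sample size is inadequate or the power statement wrong. Neither follows: t-based power is 0.82 at 15 completers. The choice should be settled before the data are unblinded, but it does not undermine the design.

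**What to change.** In Data Analyses and Interpretation, replace the rule that reports the bootstrap only when it differs with one prespecified small-sample method that is always reported for the primary contrasts. One suitable choice is GEE/WGEE with a bias-corrected (Kauermann-Carroll) sandwich variance and a t reference with df = contributing participants minus 1. For a balanced time contrast with no other terms, the correction divides the variance by 1 − 1/n, which gives Σ(d − d̄)²/(n(n−1)), so the test is the paired t test.

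Add a cluster bootstrap-t that resamples participants as a sensitivity analysis. State whether it is symmetric or equal-tailed, the number of resamples, and whether WGEE weights are re-estimated in each resample. If the team expects strongly skewed changes, it may reasonably make a bootstrap-t form primary. What matters is that one method is fixed in advance.

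The cost is one or two sentences and intervals about 10% (n = 20) to 13% (n = 15) wider than the uncorrected ones. The team should confirm that its chosen R or SAS routine provides the correction with estimated weights. N = 20 does not change.

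### The multiplicity rule defines no test family and gives the two outcomes tagged as primary no protected alpha, while the stated 0.8 power is for a single unadjusted test

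*Combined protocol and SAP*

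**What the plan says.** Section 9, Data Analyses and Interpretation, sets alpha at "0.05 for all analyses and use Holm-Bonferroni adjustments for <= 5 tests" and "False Discovery Rate (FDR) for > 5 tests". For correlated outcomes it adds that "corrections will be calculated based on the effective number of independent tests that account for correlations between the outcomes". It does not say whether tests are counted per aim, per domain, per session or over the whole study. Nor does it say whether the five-test limit refers to the nominal or the effective count.

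Under Outcome Measure(s), Primary Outcomes, two items carry a primary tag inside a longer primary list: "Pleasantness ratings of slow (primary) and fast gentle brushing" and "Pain perception assessed in response to noxious pinprick (primary), pressure, and heat stimulation". The analysis section never refers to these tags, and it has no hierarchy, gatekeeping or reserved alpha.

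The Pain perception procedures give pinprick a threshold, plus ratings of a single prick and of a 10-repetition train. Each rating uses two scales.

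Sample Size Determination & Power states that N = 20 "will provide 0.8 power to detect an effect size as small as d = 0.8 based on a two-sided" alpha of 0.05. It names no outcome and makes no multiplicity adjustment.

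**The concern.** The outcome list singles out one touch and one pain outcome, but the testing rule treats them like any other. Two things follow.

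- **Error control.** Whether a tagged outcome is tested under family-wise or false-discovery control depends on how many variables are counted with it, and the plan leaves that count open. FDR limits the expected share of false claims. It does not limit the chance of any false claim to 0.05 when some outcomes truly respond.
- **Power.** The sample size is justified at 0.05 for one test. Any multiplicity rule that makes the tagged outcomes share alpha gives less than that, and the plan does not say how much less.

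At stake is whether a positive result on slow brushing or pinprick can be read as a confirmed answer to Aim 2 or Aim 1.

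**Working it through.** **1. The plan's own figure.** Inputs are from the sample size section: d = 0.8, within-subject correlation 0.5, attrition 25%, two-sided 0.05. For a paired t-test, dz = 0.8 / sqrt(2 × (1 − 0.5)) = 0.8. With n = 15 the noncentrality is 0.8 × sqrt(15) = 3.10 on 14 df, and power is 0.821. With n = 14 it is 0.790. So 15 completers are needed, and 15 / (1 − 0.25) = 20. The stated N is reproduced, for one unadjusted test.

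**2. Counting variables.** From Specific Aims and the Pain perception procedures:

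- Pinprick: threshold, single-prick intensity and unpleasantness, train intensity and unpleasantness (5).
- Pressure: threshold (1).
- Heat: threshold, intensity and unpleasantness (3).

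Aim 1 totals 5 + 1 + 3 = 9. Slow and fast pleasantness add 2, giving 11 overall. This is a reconstruction. The outcome list does not name temporal summation, so the count could be lower. The analysis text runs models separately by session, so it could also be higher.

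**3. Exact power at n = 15 by significance level.**

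| Level | Power |
|---|---|
| 0.05 | 0.821 |
| 0.025 (first Holm step, 2 tests) | 0.717 |
| 0.01 (first Holm step, 5 tests) | 0.562 |
| 0.05/9 (strictest step, 9 tests) | 0.462 |
| 0.05/11 (strictest step, 11 tests) | 0.430 |

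**4. Simulation of the rule.** Assumptions: 40,000 trials per setting, paired tests, d = 0.8 on each real outcome, equal correlation 0 to 0.5 between outcomes, Benjamini-Hochberg (BH) for FDR, and no effective-number correction. Power is per real outcome; FWER is family-wise error.

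| Setting | Power, 15 completers | Power, 20 completers | FWER, 15 completers |
|---|---|---|---|
| BH over 11, two real | 0.50–0.51 | 0.71–0.72 | 0.07–0.09 |
| BH over 11, five real | 0.63–0.65 | 0.82–0.84 | 0.09–0.12 |
| BH over 11, all real | 0.76–0.79 | 0.91–0.92 | none null |
| BH over 9, one real | 0.47–0.48 | 0.67–0.68 | 0.06–0.07 |
| BH over 9, four real | 0.63–0.64 | 0.82–0.84 | 0.08–0.10 |
| Holm over 2, both real | 0.78–0.79 | 0.91–0.92 | none null |
| Holm over 2, one real | 0.72 | 0.86–0.87 | 0.04–0.05 |

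Hand check of Holm over two, independent outcomes, both real: 0.717 + (0.821 − 0.717) × 0.717 = 0.792.

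**5. The five-to-six step.** Five outcomes all at p = 0.03 give no Holm rejection, because the first limit is 0.05/5 = 0.01. Add a sixth at p = 0.03 and BH rejects all six, because the sixth limit is 0.05 × 6/6 = 0.05. With only two real effects (independent, 15 completers), going from Holm over 5 to BH over 6 moves power from 0.59 to 0.62 and FWER from 0.040 to 0.077. At 10 tests power is back down to 0.53.

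**The case against.** Several stronger readings are tempting, and the documents do not support them.

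- **That all primary variables are pooled into one family.** This is not written. Hypothesis testing is described aim by aim. If each aim is a family, slow and fast pleasantness stay within five tests, and slow brushing keeps Holm. This stands for touch. It does not rescue pinprick, because Aim 1 alone reaches about nine variables on a nominal count.
- **That adding outcomes makes claims easier.** This holds at the five-to-six step, or when the added outcomes themselves respond. Further null outcomes make claims harder. With a single real effect the five-to-six step lowers power (about 0.57 to 0.54).
- **That FDR causes the power loss.** At a given number of tests BH has more power than Holm. The loss comes from computing power with no adjustment and then sharing alpha.
- **That picking the best of five null pinprick variables gives an error of 0.16 to 0.23.** That would be unadjusted testing at 0.05. The plan's rule for five tests is Holm, which gives 0.04 to 0.05.

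Other points also carry weight. The effective-number clause might bring a correlated set to five or fewer and so back under Holm. But the text does not say which count drives the switch, and the type of error control would then depend on observed correlations. The low power figures need 15 completers and few real effects. The protocol also implies 16 completers (20% attrition, under Participant Randomization) or 20 (Subject Population). Family-wise error under BH stays at or below 0.05 when nothing is real, and is about 0.04 when only one outcome is null. Finally, this is a pilot, so strict confirmatory control is partly a matter of choice. Even so, the sponsor marked two outcomes as primary and stated a power, and the testing rule should match both.

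**Conclusion.** The concern holds in this form. The plan leaves the test family undefined and gives its two tagged outcomes no protected alpha. On a nominal count the pain outcome falls under FDR, and power is stated for one unadjusted test. Slow brushing keeps family-wise control only if each aim is its own family.

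With 15 completers, power for a tagged outcome can fall from the stated 0.8 to about 0.5 when few outcomes respond. It stays at 0.76 to 0.79 if all 11 do. Family-wise error is about 0.08 to 0.12 with four or five real effects. With 20 completers the 11-outcome, two-real case gives 0.71 to 0.72.

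These sizes rest on Benjamini-Hochberg, a paired contrast as in the power statement (not the per-session WGEE), d = 0.8 on each real outcome, correlation 0 to 0.5, the reconstructed counts of 9 and 11, and no effective-number correction. The gap in specification does not depend on them. This should be corrected; for a small pilot it is not a fatal defect.

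**What to change.** - Define the confirmatory family as two variables: slow-brushing pleasantness and one pinprick variable, named before unblinding (for example the mean intensity rating of the 10-repetition train, or the threshold).
- Test these two with Holm at 0.05, whatever else is tested.
- Place all other outcomes in one FDR family labelled exploratory.
- State that neither the nominal nor the effective number of tests decides the error rate for the two primaries.
- Restate power for Holm over two. With 15 completers it is about 0.78 to 0.79 per outcome if both effects are real and 0.72 if only one is. Reconcile the expected number of completers (15, 16 or 20) at the same time.

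The cost is SAP wording. Pressure, heat, fast brushing and the remaining pinprick variables can no longer be called primary, and the stated power is slightly lower. If the sponsor wants at least 0.80 for each primary whatever the other shows, the first Holm step (0.025) needs 18 completers (power 0.815; 17 gives 0.786). That means 18 / 0.75 = 24 enrolled at 25% attrition.
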